7.5.5 Missing Data

In general, missing data will not be imputed. However, more analytical details about handling of missing data may be covered in the SAP.

7.5.6 Sub-Group Analyses

The primary and sensitivity analyses of primary endpoint will be repeated by the disease severity stages.

7.5.7 Analysis of Secondary Endpoint(s)

All secondary analysis will be carried out using the Full Analysis Set.

The endpoints of proportion of patients not needing liver transplantation, without hepatic transplantation by Ganzert's intoxication (pre-treatment), without hepatic transplantation by Ganzert's intoxication (during treatment), without hepatic transplantation by INR severity criteria (INR < 2 and ≥ 2) (during treatment), without hepatic transplantation by Escudié's intoxication grade transplantation criteria (INR < 6 and ≥ 6) (during treatment) will be analyzed in the same way as the analysis of primary endpoint. The number and proportion of patients meeting the criteria will be computed and presented along with 95% CI that is computed using Newcombe-Wilson score method.

Elapsed days between amanita poisoning and start of treatment will be summarized descriptively.

The time to normality for AST, ALT, bilirubin, PT/INR, and creatinine will be analyzed using Kaplan-Meier estimation method of estimation for the survival time. 95% CI will be computed for the survival rate by using Greenwoods formula. The analysis of time to normality for AST, ALT, bilirubin, PT/INR, and creatinine will be analyzed by the disease severity stages as well.

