| | 
approximation, a sample size of 139, provides a two-sided 95% confidence interval for proportion of subjects not meeting the outcome of interest (liver transplantation and/or death) within a half width of 5% from the observed proportion at an expected proportion of 90%.
 |
| 
Statistical Methods
 | 
Demographic and Anamnestical Data:
 
All demographic and anamnestical data will be analyzed descriptively. For quantitative variables, the descriptive summary (means, medians, standard deviation, minimum and maximum) will be calculated. For qualitative data, the corresponding absolute and relative frequencies will be determined.
 
Efficacy Analysis:
 
The primary endpoint is the proportion of subjects treated with Legalon[®] SIL that do not exhibit morbidity (liver transplantation) and/or mortality (death).
 
Proportion of subjects not meeting outcome of interest (liver transplantation and/or death) will be determined. Furthermore, the corresponding 95% confidence intervals will be determined.
 
Sensitivity Analyses:
 
Subject survival rate without hepatic transplantation and/or death will be calculated for all subjects and for each stage of disease. Moreover, the corresponding 95% confidence intervals for the rate of survival will be determined. The survival time will be described by means of Kaplan-Meier estimates.
 
Secondary endpoint (efficacy):
 
 • All quantitative secondary endpoints will be analyzed descriptively. Means, medians, standard deviations, minimum and maximum will be calculated as measures of location and dispersion. • The time to normality for AST, ALT, bilirubin, PT/INR, and creatinine, if abnormal at presentation, will be determined for all subjects and for each stage of disease by means of Kaplan-Meier estimates. 
Additional summaries -- Assessment of Emergency Liver Transplantation Criteria in ALF due to Amanita Poisoning – using Ganzert’s and Escudie’s criteria. (13a.
 
 • Number (%) of subjects without hepatic transplantation by Ganzert’s intoxication (pre-treatment) • Elapsed days between amanita poisoning and start of treatment |

| | |

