transferred to a tertiary care center where liver transplant is available. Grade 4 patients have an extremely poor prognosis. There is a 90% probability of death in spite of intensive therapy. Survival usually requires a liver transplant.

Laboratory Abnormalities and Corresponding Prognostic Indication

Transaminases

Grade 1 patients show mild elevations of liver enzymes. Grade 2 patients develop a moderate rise in transaminases, usually below 5,000 IU/L but sometimes much higher. Grade 3 patients show a steep and massive rise in transaminases. There is no significant difference in the magnitude of transaminase results in Grade 4 relative to Grade 3, although in fatal cases the mean values are generally higher. A decrease of transaminase values on Day 4 is either a sign of improvement or a hepatic "burn-out" phenomenon. A massive rise in transaminases (Grade 3 and 4) does not necessarily predict a fatal outcome, whereas a mild rise in transaminases (Grade 2) generally indicates a good chance for survival.

Prothrombin Time

PT/INR is of high prognostic value. An early and steep prolongation of prothrombin time values suggests a poor prognosis. In Europe, those patients in whom prothrombin times could not be improved to values above 20-30% by substitution of clotting factors on Days 3-4 had >90% mortality. From 48 hrs after ingestion onwards, there is a significant difference between the prothrombin time of survivors in Grade 3 (>30 %) and non-survivors in Grade 4 (< 20%).

Bilirubin

On admission to the hospital, bilirubin values are normal in 90% of all cases. Elevation at this early stage (>3 mg/dL) suggests a poor prognosis. During the course of the intoxication, only about 20% of Grade 3 patients (Grade 3b) show a marked rise in bilirubin. It is possible to obtain information on the prognosis from the absolute values after Day 3. At that time, values < 5 mg/dL indicate a favorable prognosis, even if transaminases are high, while a value > 5 mg/dL indicates a severe or fatal course.

Impairment in kidney function

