3.2.2 Secondary Efficacy

Efficacy as demonstrated by time to normality of the laboratory values from start of treatment with Legalon® SIL. The laboratory values to be followed are transaminases and renal function tests (AST, ALT, bilirubin, PT/INR, creatinine, lactic acid).

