5.5 Concomitant Medications

All concomitant medications taken during the study (from signing informed consent to discontinuation of study drug) must be recorded with indication, daily dose, and start and stop dates of administration in the CRF.

Medications taken within 28 days prior to screening and prior to dosing with study medication will be documented as a prior medication. Medications taken after dosing begins with study medication will be documented as concomitant medications.

There are no prohibited medications for this study.

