6.3.1 Required Daily Study Assessments/Procedures While on Study Treatment

- Physical
- Vital signs
- AST
- ALT
- ALP
- Bilirubin
- PT
- INR
- BUN
- Creatinine
- Lactate
- Amylase
- Ammonia
- CBC with differential

- Platelets
- Glucose
- Na
- K
- AEs
- Concomitant medications
- Infusion of Legalon® SIL
- Other measures to eliminate residual toxin, maintain perfusion and vital signs, and prevent coagulopathy will be at the discretion of the OSI.

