7.4 Secondary Endpoint (s)

The secondary endpoints of the study are:

- Proportion of patients not needing liver transplantation
- The time to normality for AST, ALT, bilirubin, PT/INR, and creatinine during the treatment period
- Number (%) of patients without hepatic transplantation by Ganzert's intoxication (pre-treatment)
- Elapsed days between amanita poisoning and start of treatment
- Number (%) of patients without hepatic transplantation by Ganzert's intoxication (during treatment)
- Number (%) of patients without hepatic transplantation by INR severity criteria (INR < 2 and ≥ 2) (during treatment)
- Number (%) of patients without hepatic transplantation by Escudie's intoxicion grade transplantation criteria (INR < 6 and ≥ 6) (during treatment)

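### Time to normal PT/INR and creatinine has no rule for values obtained under clotting-factor or renal support, so a supported normal value can count as recovery on the drug

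*Combined protocol and SAP*

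**What the plan says.** Section 3.2.2 sets the purpose of the endpoint: "Efficacy as demonstrated by time to normality of the laboratory values from start of treatment with Legalon® SIL". Section 7.4 lists it as "The time to normality for AST, ALT, bilirubin, PT/INR, and creatinine during the treatment period". Section 7.5.7 gives the method: "The time to normality for AST, ALT, bilirubin, PT/INR, and creatinine will be analyzed using Kaplan-Meier estimation method", with Greenwood confidence intervals, in the Full Analysis Set, overall and by disease severity stage. The synopsis (Statistical Methods) adds the one condition: the time, "if abnormal at presentation, will be determined for all subjects and for each stage of disease by means of Kaplan-Meier estimates".

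On background care, Section 6.3.1 says: "Other measures to eliminate residual toxin, maintain perfusion and vital signs, and prevent coagulopathy will be at the discretion of the OSI". The synopsis (Methodology and treatments) leaves the same measures to the treating physician, within best practice. Section 5.5 states: "There are no prohibited medications for this study". It asks that medications "must be recorded with indication, daily dose, and start and stop dates of administration in the CRF".

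Section 2.2 (Prothrombin Time) describes patients whose prothrombin times "could not be improved to values above 20-30% by substitution of clotting factors on Days 3-4 had >90% mortality". Section 2.2 also expects renal failure with possible oliguria or anuria in some patients. Table 1 schedules INR and creatinine every 6 hours until discharge or as indicated.

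**The concern.** PT/INR and creatinine are read here as markers of hepatic and renal recovery. Plasma, clotting-factor products and renal replacement can move the measured value without any recovery of the organ. If the event is simply a normal result, a patient with continuing liver injury whose INR is normal at a draw taken after plasma contributes an event, and an early one given 6-hourly sampling.

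The error has a direction: a supported normal value can only bring the apparent event forward. It should also be uneven across stages. By the definitions in Section 2.2, the higher grades have the more marked coagulopathy (INR above 2.0 in Grade 3, above 3.0 in Grade 4) and Grade 4 has renal dysfunction, so these patients are the likeliest to be supported. Section 7.5.7 reports curves by stage, where a few such events can shift a small stratum. At stake is the meaning of two of the five laboratory endpoints in Section 7.4: they would partly describe the use of support rather than recovery.

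**Working it through.** **1. The plan's own figure.** The only figure that can be reproduced is the sample size in Section 7.1, which rests on the primary proportion: n = z² p(1 − p)/d² = 1.96² × 0.90 × 0.10 / 0.05² = 138.29, rounded up to 139. The half width at 139 is 0.0499. It is correct, and this point does not touch it. No figure is given for time to normality.

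**2. What decides whether a supported value counts.**
- Abnormal at presentation: required (synopsis).
- Sustained normality: not mentioned.
- Normality free of support: not mentioned.
- Censoring, exclusion or flagging of values under support: not mentioned. Section 7.5.5 covers missing data only, and a supported value is not missing.
- Limits on clotting-factor support: none (synopsis; Sections 5.5 and 6.3.1).
- Limits on renal replacement: none stated. Dialysis is not named, so this is read from silence.
- Whether support moves the value: Section 2.2 treats prothrombin time as improvable by substitution, and says prerenal azotemia can usually be reversed by fluids.

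Nothing in this list stops a supported normal value from being an event.

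**3. Size, under assumptions only.** The documents give no rate of plasma, clotting-factor or dialysis use. Assume that true recovery is exponential with median m, and that a share s of patients with an abnormal value has a support-produced normal value at a time uniform on 12 to 72 h. The apparent proportion not yet normal at time t is

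S(t) = 2^(−t/m) × [1 − s × U(t)], with U(t) = (t − 12)/60 between 12 and 72 h, and 1 after that.

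At 96 h, U = 1, so the apparent proportion normal is 1 − (1 − s) × 2^(−96/m). The apparent median solves S(t) = 0.5. For m = 96 h:

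| s | Apparently normal by 96 h | Apparent median |
|---|---|---|
| 0 | 50% | 96 h |
| 5% | 1 − 0.95 × 0.5 = 52.5% | 96 × log2(1.9) = 89 h |
| 10% | 1 − 0.90 × 0.5 = 55% | 96 × log2(1.8) = 81 h |
| 20% | 1 − 0.80 × 0.5 = 60% | about 68 h (S is 0.503 at 67 h and 0.498 at 68 h) |
| 30% | 1 − 0.70 × 0.5 = 65% | 59 h |

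With s = 20%, an assumed true median of 72 h moves the 96 h proportion from 60% to 68%, and one of 120 h moves it from 43% to 54%. The direction is the same throughout.

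**4. Patients, not events.** Here s is a share of patients with an abnormal value. If 20% to 40% received support and half of those showed a transient normal value (both assumed), s would be 0.20 × 0.5 = 10% to 0.40 × 0.5 = 20%. As a share of events it would be larger unless every patient has an event: if half of the others normalised, 0.10/(0.10 + 0.90 × 0.5) = 18% to 0.20/(0.20 + 0.80 × 0.5) = 33%.

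**The case against.** The strongest reply has four parts.

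First, Section 7.5.7 does not define the event, and Section 7.5 defers detailed methodology to a separate SAP that is not in the document reviewed. That the event is the first normal value is the natural reading of a Kaplan-Meier time to normality, not stated text. This stands as a limit on the wording. It does not remove the point, because the protocol followed as written has nothing that excludes a supported value.

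Second, the prothrombin passage in Section 2.2 concerns patients who did not respond to substitution, and it does not say that substitution reaches the normal range. This is also fair. It shows that the protocol regards the value as movable, not how often it becomes normal.

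Third, time to normality under drug plus best supportive care is a legitimate quantity. It is, but Section 3.2.2 labels the result as efficacy of the drug. Showing both curves serves both readings.

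Fourth, the endpoint is secondary and descriptive, and without a control arm no definition separates drug from background care. This stands and limits the weight of the point.

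A reader might also infer that the data are beyond repair, because Section 5.5 asks for dates rather than clock times and covers medications rather than procedures. The documents do not support that: Section 8 gives full access to source documents, Section 8.1 has sites supply copies of them, and Section 9.2.2 records actions taken in treating adverse events. Nor does the earlier end of medication recording in Section 5.5 (at drug discontinuation, against the Follow-up Visit in the synopsis and Table 1) undermine this endpoint as defined, since Section 7.4 limits it to the treatment period. That conflict should be reconciled separately.

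**Conclusion.** The point holds in a limited form. Time to normal PT/INR and creatinine is presented as drug efficacy with no condition except abnormality at presentation, while support that can move these values is unrestricted. A PT/INR normal only under clotting-factor support would, on the natural reading, count as recovery and shorten the apparent time. The PT/INR part rests directly on the text; the creatinine part is inferred, because renal replacement is never named.

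The size is unknown. The illustrative shift in median from 96 h to about 81 or 68 h rests on an assumed recovery curve, assumed timing of supported values, and 10% or 20% of patients affected. It should not be quoted as a proportion of false events.

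Two further inferences are not supported. Patients on vitamin K antagonists appear nowhere in the documents, so there is no basis for excluding them. Nor is a mandatory rule of two consecutive normal values warranted: the synopsis and Section 6.3 tie drug discontinuation to normal PT/INR together with transaminases at or below twice the upper limit, and with the endpoint confined to the treatment period such a rule could discard true recoveries.

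The change is worth making. The primary endpoint and N = 139 are unaffected.

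**What to change.** In Sections 7.4 and 7.5.7, state that a normal PT/INR obtained within a sponsor-fixed window after plasma or a clotting-factor product counts as not yet normal, with follow-up continuing. State the same for a normal creatinine within such a window after renal replacement. Report the curve using all values alongside, overall and by stage.

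Choose the window to fit the 6-hourly sampling and the length of the treatment period. So that true recoveries are not lost, let laboratory values already collected after drug stop or at follow-up confirm normality. This needs a sentence in Section 7.4, which now confines the endpoint to the treatment period. Table 1 marks INR at the follow-up visit but not creatinine, so for creatinine the later values would be those taken up to discharge.

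In the CRF, record the times of clotting products and of renal replacement from the hospital chart, for as long as laboratory values count towards the endpoint.

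The cost is some SAP and protocol wording and a few chart-derived fields. The price in results is somewhat longer times to normality and a few fewer events. The change concerns the analysis only and alters no treatment or stopping rule.

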7.6 Interim Analyses

Interim Clinical Study Report summarizes the data related to the first 50 patients of the 54 recruited, as of December, 2012 into this study with protocol No. SB16A1.07, entitled "Prevention and Treatment of Amatoxin Induced Hepatic Failure with Intravenous Silibinin (Legalon® SIL): An Open Multicenter Clinical Trial", which was originally submitted to the FDA on 9 July 2009 under IND 105,960 and is being conducted in US investigational sites. Study Objectives and Endpoints: This study aims to assess the efficacy and safety of Legalon® SIL in the prevention of severe morbidity (defined as liver transplant) and death in amatoxin poisoned patients. The primary endpoint is the proportion of enrolled patients without liver transplant or death. Secondary assessments include AST, ALT, bilirubin, PT/INR, and creatinine as indicators of liver and renal function, adverse events and vital signs.

Design: Multicenter, open, uncontrolled study.

Study Population: Patients with a clinical diagnosis of amatoxin poisoning based on history, gastrointestinal symptoms, elevated liver enzymes.

Results: 42 of the 50 poisoned patients (84.0%; 95% CI 70.9% to 92.8%) were discharged home from the hospital with complete recovery. Conversely, 8 of the 50 patients (16%) had a severe morbidity, resulting in 5 deaths and 3 liver transplants. The negative outcome of these 8 patients was due to the progression of the liver and renal failure as a consequence of Amatoxin intoxication in the absence of an adequate aggressive hydration to preserve renal function and when treatment with Legalon® SIL was instituted started >96 hours after poisoning.

A total of 11 patients (22.0%) experienced 20 Adverse Events (AEs) during the course of the clinical trial, 11 of which were Serious Adverse Events (SAEs). All SAEs were regarded as severe AEs by the on-site investigator (OSI) and all of them were considered not related to Legalon® SIL treatment. Indeed, they were all signs of the severe amatoxin intoxication, responsible for severe liver failure leading these patients to die or to be liver transplanted.

Conclusions: Since silibinin strongly inhibits the hepatocyte uptake of amatoxin and the survival has been correlated with the time of initiation of therapy, Legalon® SIL treatment should be instituted as soon as a diagnosis has been made/suspected. As a matter of fact, all the patients who started treatment with the study drug >96 hours after poisoning had a negative outcome.

As long as renal function has been maintained with aggressive intravenous hydration, patients who receive intravenous Legalon® SIL appear to recover from amatoxin induced hepatotoxicity in a rapid, predictable, and reliable manner. Length of hospitalization for the successfully treated patients was relatively short, often well under 8 days. Legalon® SIL was not associated with any serious adverse events. It was easy to administer, safe, and was well tolerated in this patient population.

7.7 Safety Analyses

The safety analyses will be based on the Safety population.

The analysis set for safety summaries is defined as all subjects who received at least one dose of study medication.

7.7.1 Adverse events

Adverse events will be summarized and listed by Preferred Term (PT) and SOC using MedDRA vocabulary (most recent) by treatment. All AEs that occur after the first dose of study medication through 30 days after the last dose will be considered to be treatment emergent AEs. The number and percentage of subjects with at least one treatment emergent AE will be presented by treatment group and events further summarized by maximum severity and relationship to study medication. The number and percentage of patients with SAE, discontinuation of study treatment due to AE (DAE), and AEs of severe intensity will be summarized by treatment. The AEs will be summarized by outcome of the event as well. Furthermore, listings of SAEs and AEs that lead to withdrawal will be provided. Summary statistics (N, %) of AEs of special interest will be also be separately tabulated.

Descriptive statistics will be provided for the following safety data. No inferential analysis of this safety data is planned. Any ECG, BP, and pulse rate abnormalities of potential clinical concern will be described.

7.7.4 Laboratory Data

Clinical laboratory data consists of clinical chemistry, hematology, and other parameters. These data will be summarized by treatment. For clinical laboratory tests, listings of values for each patient will be presented with abnormal or out of range values flagged. The laboratory data will be presented in System International (SI) units. Numerical laboratory results will be summarized using standard summary statistics by timepoint of collection and treatment group. Baseline shift tables will be prepared for the laboratory findings ('Normal', 'Low' and 'High'). Subject listing will be prepared for the pregnancy test results for female patients.

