1 STUDY SCHEDULE OF ACTIVITIES

The Schedule of Activities table provides an overview of the protocol visits and procedures. Refer to the Study Conduct Section (6) for detailed information on each procedure and assessment required for compliance with the protocol.

Table 1 Study Schedule

Schedule of Events

| PHASE | SCREENING PHASE | | Dosing | TREATMENT PHASE | | FOLLOW-UP PHASE |
|------------------------------|----------------------------|------------------|--------|---------------------------------------------------------------------------|---------------------------------------------|-----------------|
| | Screening/ Presentation | Pre -First dose* | | Every 6 hours post first dose until discharge or as indicated (+/-1 hour) | Every 24 hours post first dose (+/-2 hours) | |
| Informed consent | X | | | | | |
| History | X | | | | | |
| Physical/ Review of Systems | X | X | | | X | X |
| Vital Signs | X | X | X | | | X |
| CBC, Differential, Platelets | X | X | X | | | |
| Transaminases (AST, ALT) | X | X | X | | | X |
| ALP | X | X | X | | | X |
| Ammonia | X | X | X | | X | X |
| Lactate | X | X | X | | | |
| Amylase | X | X | X | | | X |
| Lipase | X | X | X | | | X |
| Bilirubin (total) | X | X | X | | X | X |
| PT | X | X | X | | X | X |

| PHASE | SCREENING PHASE | | TREATMENT PHASE | | | FOLLOW-UP PHASE |
|--------------------------------------------------------------------------------------------------------------------------|----------------------------|------------------|-----------------|---------------------------------------------------------------------------|---------------------------------------------|-------------------------------------------------------------|
| | Screening/ Presentation | Pre -First dose* | Dosing | Every 6 hours post first dose until discharge or as indicated (+/-1 hour) | Every 24 hours post first dose (+/-2 hours) | |
| Event | | | | | | At Follow-up, 10 (+/- 2) Days after study drug discontinued |
| INR | X | X | | X | | X |
| BUN, Creatinine, GFR | X | X | | X | X | |
| Glucose | X | X | | X** | X | |
| Electrolytes (NA, K, Cl, CO2) | X | X | | X | | |
| Serum Pregnancy test for woman of child bearing potential | X | | | | | |
| Loading dose Legalon-SIL 5mg/kg IV over 1 hour followed by continuous IV infusion of 20 mg silibinin/kg over 24 hours | | | X | | | |
| Adverse Events | X | X | X | X | X | X |
| Concomitant Medications | X | X | X | X | X | X |

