3.2.1.1 Safety

Safety based on the evaluation of changes in baseline laboratory and clinical presentation while on study treatment. The laboratory values to be followed are transaminases and renal function tests (AST, ALT, bilirubin, PT/INR, creatinine, lactic acid).

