6.3 Treatment phase

Following receipt of study drug, if patient remains eligible for enrollment according to the protocol, treatment with Legalon® SIL should begin as soon as possible as a continuous infusion until the PT/INR have returned to the normal range set by the institution and transaminases have returned to no greater than 2 times the institutions upper limit of normal. If the laboratory tests and/or the patient clinical picture is not improving after 96 hours on treatment the PPI and OSI must specifically discuss the benefit of continued treatment. Full documentation and reason for decision to either continue or discontinue treatment must be documented in the patient's medical record as well as on the Daily Communication CRF.

Every effort should be made to ensure that the protocol required tests and procedures are completed as described. However, it is anticipated that from time to time there may be circumstances, outside of the control of the investigator that may make it unfeasible to perform the test. In these cases, the investigator or designated representative will take all steps necessary to ensure the safety and well-being of the subject. When a protocol required test cannot be performed the investigator or designated representative will document the reason for this and any corrective and preventive actions which he/she has taken to ensure that normal processes are adhered to as soon as possible. The Mylan study team will be informed of these deviations in a timely fashion.

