6.4 Follow-up Phase

Patients will be followed 10 days +/-2 after stopping Legalon® SIL therapy unless they failed treatment and proceeded to transplant. Follow up will consist of a physical examination and blood work to assure recovery and to assess for any AEs.

Subjects will be reminded that SAEs should be reported to the study staff up to 30 days after the last dose of study medication.

If the patient recovers from the poisoning, upon discharge from the hospital, they should be given a prescription for follow up blood work to include PT/INR and liver function studies as well as instructed to follow with their local physician for a physical exam. The OSI or designee is responsible for following up with the patient for the results of the exam and blood work.

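### Numeric laboratory results are summarised only by time point among those still sampled, so later columns mix real change with changing membership, and no numeric change from baseline is planned

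*Combined protocol and SAP*

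**What the plan says.** Section 7.7.4 gives one summary of numeric laboratory values: "Numerical laboratory results will be summarized using standard summary statistics by timepoint of collection and treatment group". The trial has one arm, so in practice this is a single set of columns over time. The same section adds "Baseline shift tables will be prepared for the laboratory findings ('Normal', 'Low' and 'High" and per-patient listings with out-of-range values flagged.

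Section 3.2.1.1 defines the safety endpoint: "Safety based on the evaluation of changes in baseline laboratory and clinical presentation while on study treatment".

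Four other places decide who contributes a value at each time point:

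- The frequent in-hospital column of Table 1 (section 1) is headed "Every 6 hours post first dose until discharge or as indicated (+/-1 hour".
- Section 6.3.1 lists a daily panel under the title "Required Daily Study Assessments/Procedures While on Study Treatment".
- Section 6.3 continues treatment "until the PT/INR have returned to the normal range set by the institution and transaminases have returned to no greater than 2 times" (the multiple refers to the local upper limit).
- Section 6.4 states: "Patients will be followed 10 days +/-2 after stopping Legalon® SIL therapy unless they failed treatment and proceeded to transplant".

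On missing values, section 7.5.5 says "In general, missing data will not be imputed" and leaves further detail to the SAP. Section 7.5 makes one exception: a missing baseline is filled from screening.

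**The concern.** A mean at a given hour describes a patient's course only if the same patients are in every column. Here a patient leaves scheduled on-treatment sampling on recovery, transplant or death, and all three are tied to the laboratory values. Departure of recovered patients pushes later means towards the sick; departure of deaths and transplants pushes them the other way. The follow-up column is drawn essentially from transplant-free survivors.

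There is no control arm in which the same artefact would appear and so reveal itself. A reader is likely to take the columns as the course on drug, and to read a late drift as toxicity, or a near-normal follow-up column as recovery of the whole cohort. The planned number also does not measure what section 3.2.1.1 defines, which is change from baseline.

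**Working it through.** **Figures from the plan.** No stated figure is disputed. The interim results in section 7.6 supply the outcome mix: 42/50 = 84.0% recovered, and 5 deaths + 3 transplants = 8/50 = 16%. The exact (Clopper-Pearson) interval for 42/50 is 70.9% to 92.8%, as printed. The documents give no patient-level laboratory values or discharge times, so everything below is illustration.

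**Step 1: can membership alone move a mean?** Assume INR stays constant in every patient, at 1.5 if recovering and 4.0 if failing.

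- All 50 sampled: (42×1.5 + 8×4.0)/50 = 1.90.
- Half of the recovering patients gone, all failures still sampled: (21×1.5 + 8×4.0)/29 = 2.19.
- Half of both groups gone: (21×1.5 + 4×4.0)/25 = 1.90.
- Only recovered patients seen, as at follow-up: 1.50.

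The mean can rise, stay level or fall with no patient changing. Which of these happens depends on the relative speed of departure in the two groups.

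**Step 2: how fast might the mix change?** Assumptions: 16% failures, leaving uniformly between 48 and 240 h; recovering patients have log-normal peak transaminases at 24 h (median 1500 IU/L, log-SD 0.8), halve every h hours and leave at 80 IU/L. Per 100 patients, for t from 48 to 240 h:

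- failures still sampled: F(t) = 16 × (240 − t)/192
- recovering patients still sampled: R(t) = 84 × Φ([ln(1500/80) − (t − 24) ln 2 / h]/0.8)
- share of failures: F/(F + R)

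At 120 h with h = 18: F = 16×120/192 = 10.0; R = 84×Φ([2.931 − 3.697]/0.8) = 84×Φ(−0.957) = 14.2; share = 10.0/24.2 = 41%.

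| Halving time | 24 h | 96 h | 120 h | 144 h |
|---|---|---|---|---|
| 18 h | 16% | 20% | 41% | 85% |
| 24 h | 16% | 14% | 17% | 27% |
| 36 h | 16% | 13% | 12% | 11% |

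The result is sensitive to the assumed spread: with h = 18, the 120 h share is 54% at log-SD 0.6 and 35% at log-SD 1.0. The 85% cell describes few patients: F + R = 8.0 + 1.5 = 9.5 per 100, or about 13 of 139.

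**Step 3: who can be in the follow-up column?** Of the 8 interim failures, the 3 transplants are exempt under section 6.4, and the 5 deaths cannot contribute if they preceded the visit. On that basis the column holds at most 42/50 = 84% of treated patients.

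**Step 4: do the other outputs give the missing number?** Section 4.3.1 requires AST or ALT above the upper limit at entry, so at least one of them starts as High. The grade boundaries in section 2.2 (1000 and 5000 IU/L) both lie within High. A patient going from 200 to 6000 IU/L and one going from 6000 to 200 IU/L would both be counted as High to High. Listings show each patient but are not a summary. Kaplan-Meier time to normality (section 7.5.7) gives timing, not size of change, and omits lactic acid, which section 3.2.1.1 lists.

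**The case against.** The strongest reply is that the time-point table is not the only route to a signal. Shift tables and flagged listings follow the individual. Five of the six laboratory measures in section 3.2.1.1 also get Kaplan-Meier time to normality, overall and by severity stage. Clinically significant laboratory changes are recorded as adverse events and summarised by maximum severity and relationship. The table is descriptive, section 7.7.1 plans no inference on safety data, and section 7.5 leaves detailed methods to a SAP. All of this stands and keeps the point small. It does not supply a numeric change from baseline.

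A second reply is that the effect is slight while most patients are still sampled. In the model the share of failures at 96 h is 13% to 20% against 16% at the start. This also stands; the later columns are the exposed ones, and they may be sparse, since section 7.6 describes recovered patients' stays as often well under 8 days.

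Three further limits stand. Twice the upper limit of normal is part of the rule for stopping drug, not a discharge rule, and Table 1 allows sampling as indicated, so the model's exit rule is a simplification. Recovered patients are sampled again at about day 10. The follow-up visit is off treatment and so falls outside the on-treatment wording of section 3.2.1.1.

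A reader might go further and infer that the trends are purely an artefact, or that a late inpatient rise is bound to appear. The documents do not support either. Real change also enters every mean, and with a 36 h halving time the share of failures falls. Nor is it right that nothing is imputed, given the baseline rule in section 7.5.

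**Conclusion.** The point holds as a minor one. Section 7.7.4 summarises numeric results only by time point, among a group whose membership depends on the same laboratory values, and plans no numeric change from baseline although the safety endpoint is defined by change. Later columns cannot be read as the course of a fixed set of patients.

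Neither the sign nor the size of the effect can be fixed from the documents. The 12% to 41% range at 120 h rests on assumed peaks, spread, halving times and exit times, with only the 16% failure rate taken from the interim report. The statement that no interim failure would appear at follow-up further assumes that all five deaths came before the visit and that exempt patients had no laboratory tests then.

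The primary endpoint and the efficacy analyses do not use this table and are not affected.

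**What to change.** In section 7.7.4, or in the SAP that section 7.5 calls for:

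1. At each time point, show n and the paired change from baseline in patients with both values, split by final outcome (recovered; transplant or death). The split is descriptive and should not be read as a drug effect.
2. Over all treated patients, add each patient's worst post-baseline value and its change from baseline. State that the worst value also reflects the natural course of the poisoning.
3. Label the follow-up column as essentially transplant-free survivors, with its n.

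Two alternatives are best avoided. Change to the last on-treatment value should not be the main summary, because the stopping rule builds in improvement for recovered patients. A minimum-percentage cut-off for showing a time point would be arbitrary, and one set at 80% could remove the follow-up column, which holds at most 84% at interim rates.

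The cost is some SAP wording and a few extra descriptive tables from data already collected. No sampling, treatment or follow-up rule changes.
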